Study design: multicenter, randomized, double-blind, placebo-controlled, parallel-group, dose-ranging study of 12-week treatment with 3 doses of luseogliflozin or placebo on top of metformin

The study will consist of 3 periods: selection period up to 2 weeks, double-blind treatment period with 4 parallel groups (doses 2.5 mg, 5 mg, 10 mg of luseogliflozin and placebo) on top of metformin for 12 weeks and the follow up period for 2 weeks after double blind treatment stop.

Number of participants:

Planned: 320 patients included into the study and randomised using Interactive Response System (IRS) with a randomization ratio 1:1:1:1 (80 patients in 2,5 mg Luseogliflozin group; 80 patients in 5mg Luseogliflozin group; 80 patients in 10 mg Luseogliflozin group; 80 patients in placebo group)

Diagnosis and main criteria for selection:

Out-patients (male and female) of Caucasian race aged 18-75 years inclusive with type 2 diabetes mellitus (diagnosed for not less than 3 months prior to selection), treated with metformin in stable dose equal or more than 1500 mg daily for at least 3 months and with inadequate glycemic control (HbA1c 7.5 %-10.0 % at

Name of the sponsor: JSC Servier	Individual Study Table Referring to Part of the Dossier	(For National Authority Use only)
Name of Finished Product:	Volume:	
Name of Active Ingredient: Luseogliflozin	Page:	

central laboratory).

Body mass index less than 36 kg/m2,

Absence of any severe, uncontrolled conditions incompatible with study treatment or likely to interfere with the conduct of the study.

Test drug:

Name: Luseogliflozin

Dosage form: film-coated tablet

Dosages: 2,5 mg; 5 mg of luseogliflozin

Comparator:

Placebo

Dosage form: film-coated tablet

Dose regime:

Patients will have to take 3 tablets once daily orally before breakfast starting next day after inclusion visit and ending at Week 12 visit.

IMP intake will be as follows:

2.5 mg group: one tablet of Luseogliflozin 2.5 mg, one tablet of Placebo 2.5 mg and one tablet of Placebo 5 mg

5 mg group: two tablets of Luseogliflozin 2.5 mg and one tablet of Placebo 5 mg

10 mg group: two tablets of Luseogliflozin 2.5 mg and one tablet of Luseogliflozin 5 mg

Placebo group: two tablets of Placebo 2.5 mg and one tablet of Placebo 5 mg

Duration of treatment:

Selection period: no study treatment during 1-2 weeks

Double blind treatment period:12 weeks

Follow up period: no study treatment 2 weeks after double-blind treatment stop

Criteria for evaluation:

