6.3.1. Rescue treatment for loss of glucose control

The patients with loss of glucose control according to the following criteria will be prescribed rescue treatment during the double blind period of the study and will be allowed to remain in the study:

- Week 1-4: glucose level at SMBG or at the visit 240-270 mg/dl (13.3-15.0 mmol/l) inclusive after overnight fast or >400 mg/dl (>22.2 mmol/l) in a randomly performed measurement
- Week 4-12: glucose level at SMBG or at the visit 220-270 mg/dl (12.2-15.0 mmol/l) inclusive after overnight fast or >400 mg/dl (>22.2 mmol/l) in a randomly performed measurement

Insulin therapy may be instituted as needed. Alternatively, at the discretion of the Investigator, other antidiabetic medication can be prescribed; SGLT 2 inhibitors are not allowed as rescue therapy.

A complete final evaluation should be made before initiation of rescue therapy, if possible. Information to be collected should be as at Week 12 visit as indicated in Table 1 5.7.2

The details of rescue medications should be recorded in the e-CRF.

In case of hypoglycaemia that may put the patient on risk (e.g. repeated symptomatic hypoglycaemia or major hypoglycaemia), appropriate dose adjustment of antidiabetic therapy such as dose reduction/discontinuation of ongoing rescue medication or existing background therapy should be imitated. Reduction or discontinuation of ongoing rescue medication should be considered before a reduction in the dose of existing background therapy.

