- Frequency of adverse events related to the conditions of the protocol;
- Frequency of any adverse events leading to treatment withdrawal;
- Frequency of all AE of Special Interest and frequency of each individual AEOSI;
- Laboratory parameters by visit;
- Frequency of laboratory parameter abnormalities by visit;
- Vital signs (HR, SBP, DBP) by visit;
- Frequency of vital signs (HR, SBP, DBP) abnormalities by visit;
- 12-lead ECG results by visit;
- Frequency of 12-lead ECG abnormalities by visit.

Frequency data will be compared between the groups using exact Fisher tests; numeric data will be compared between the groups using the t-test or Wilcoxon-Mann-Whitney test on ranks depending on the normality of the parameter distribution (which will be tested using Shapiro-Wilk test). Laboratory parameters, vital signs and 12-lead ECG data will be analysed using two-way ANOVA (or ANOVA on ranks, if the distribution is not meeting the normality criteria) to account for group and visit factors simultaneously.

Interim analysis

No interim analysis is planned for this study.

Study populations

- Randomized Set (RS):

All patients to whom a therapeutic unit was randomly assigned using IRS.

- Per Protocol Set (PPS):

All the patients of the RS that do not have any significant protocol deviations. List of deviations will be reviewed for the determination of their significance prior to the database lock and randomization list unblinding.

- Safety Set (SS):

All patients having taken at least one dose of study drug.

- **Pharmacokinetic set**: all patients for whom blood samples were collected with no deviations that might affect the pharmacokinetic interpretation

- **Pharmacokinetic/Pharmacodynamic set:** all included patients for whom blood samples and 24-hour urinary glucose measurements were collected with no deviations that might affect the PK and/or PD interpretations.

Significance level:

The type I error of the statistical tests will be set at 5% (two-sided situation).

Multiplicity issues:

In order to take into account the multiplicity of comparisons associated with the primary objective of the study (demonstration of superiority of at least one luseogliflozin dose as compared to placebo on the primary efficacy endpoint); a Bonferroni correction will be used for the primary analysis.

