10.2. Determination of sample size

The determination of the sample size was performed considering the primary endpoint, the HbA1c.

It was estimated on the change from baseline at W12, for a difference objective between at least one dose of luseogliflozin and placebo, based on a two-sided Student's t-test for independent samples and using the Bonferroni correction in order to maintain the experiment wise type I error at 5% (bilateral situation).

About 80 patients per treatment group (320 overall) allow to conclude that at least one dose of luseogliflozin is superior to placebo with a power of around 85% if the true difference is 0.6% for a standard deviation of 1.1 %.

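### Hypoglycaemia is compared between arms without separating events that follow rescue, which is expected to favour luseogliflozin if placebo patients are rescued more often

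*Protocol*

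**What the plan says.** Protocol Section 6.3.1 keeps patients who lose glucose control in the study and has them prescribed rescue: "Insulin therapy may be instituted as needed", or another antidiabetic at the investigator's discretion, SGLT2 inhibitors excepted. Details of the rescue drug go into the e-CRF.

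Section 8.9.1 has adverse events reported from the first dose to the patient's final visit, with no cut at rescue. The Safety Set in Section 10.1 is every patient who took at least one dose. The safety parameters, analysed by group, include "Frequency of all AE of Special Interest and frequency of each individual AEOSI", and "Frequency data will be compared between the groups using exact Fisher tests". Hypoglycaemia is the first event of special interest listed in Section 8.6.

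For HbA1c, Section 10.1 does deal with rescue. The main analysis replaces post-rescue values by multiple imputation, to estimate the drug's effect free of rescue. A second analysis keeps those values as a treatment-policy estimate. Nothing comparable is stated for safety.

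**The concern.** Rescue follows from high glucose and may consist of drugs, insulin included, that lower it. Section 6.3.1 recognises that rescue drugs can contribute to hypoglycaemia, because it has them cut back before background therapy when risky hypoglycaemia occurs. By then the event already counts in the randomised arm. If more placebo patients are rescued, more rescue-induced hypoglycaemia is credited to placebo.

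The sample size assumes a true HbA1c advantage ("with a power of around 85% if the true difference is 0.6% for a standard deviation of 1.1"), so more rescue on placebo is the direction the trial itself expects. Rescue need not be rare either. Section 5.5 excludes confirmed fasting glucose only above 240 mg/dl, while the Section 6.3.1 rescue range from Week 4 begins at 220 mg/dl. A patient who enters between these values and does not improve therefore qualifies for rescue. (This is an observation about frequency; no change to either threshold is suggested.)

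Assessing the safety of the three doses is a secondary objective (Section 3). What is at stake is whether a real excess of hypoglycaemia on luseogliflozin could be diluted or hidden in the only stated comparison.

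**Working it through.** **The plan's own figure.** The only relevant quantitative statement is the power. With 80 per arm, difference 0.6, SD 1.1 and two-sided alpha 0.05/3, the standardised difference is 0.6 / (1.1 × √(2/80)) = 3.45 and the critical value is 2.39. Power is Φ(3.45 − 2.39) ≈ 85.4% (84.7% with the noncentral t on 158 df). The stated 85% reproduces. It concerns HbA1c and says nothing about safety.

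**Inputs for the safety question.** The protocol gives none, so all of these are assumptions:
- rescue rate r: 5–20% on placebo, 2–5% on a luseogliflozin arm;
- q, the probability that rescue causes hypoglycaemia in a rescued patient: 10–30%, equal in all arms;
- h, hypoglycaemia without rescue: 2–5% on placebo, 2–10% on luseogliflozin.

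**Formula.** All-events risk in an arm = h + (1 − h) × r × q. The shift is the all-events difference (luseogliflozin minus placebo) minus the rescue-free difference.

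With h = 2% on placebo and 5% on luseogliflozin (rescue-free difference +3.0 points, risk ratio 2.5):

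| r placebo / luseo, q | Placebo | Luseogliflozin | Difference | Shift | Patients of 80 | Risk ratio |
|---|---|---|---|---|---|---|
| 5% / 2%, 10% | 2.49% | 5.19% | +2.70 | −0.30 | 0.24 | 2.08 |
| 10% / 3%, 30% | 4.94% | 5.86% | +0.92 | −2.08 | 1.67 | 1.19 |
| 20% / 5%, 30% | 7.88% | 6.43% | −1.45 | −4.45 | 3.56 | 0.82 |

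For example, in the last row placebo is 0.02 + 0.98 × 0.20 × 0.30 = 0.0788 and luseogliflozin is 0.05 + 0.95 × 0.05 × 0.30 = 0.0643. With rescue-free rates of 2% in both arms, or 5% against 10%, the shift again runs from about 0.3 to 4.4 points.

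**How far the equal-q assumption matters.** The shift vanishes when q on luseogliflozin divided by q on placebo equals (1 − h placebo) × r placebo / [(1 − h luseo) × r luseo]. For the three rows this is 0.049/0.019 = 2.6, 0.098/0.0285 = 3.4 and 0.196/0.0475 = 4.1. Rescue would have to be about 2.6 to 4.1 times as likely to cause hypoglycaemia on luseogliflozin as on placebo before the direction changed.

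**What the test can show.** For 5% against 2% with 80 per arm, a two-sided 5% Fisher test has about 6% power even without bias. The comparison will be read from the estimates, which is where the shift acts.

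**Other events of special interest.** Section 8.6 links polyuria, pollakiuria and ketoacidosis to luseogliflozin's own action, and SGLT2 inhibitors are barred as rescue. The protocol gives no route by which other rescue drugs would raise these, volume depletion, or urinary and genital infections on placebo. The expected shift is about zero. The pooled frequency is affected only through hypoglycaemia, and by no more than the hypoglycaemia shift, since a patient with another such event is already counted.

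**The case against.** The strongest reply is that this is detail for the SAP. Section 10.1 calls itself brief and defers to the SAP, does not define an emergent event, and nowhere requires that post-rescue events be pooled. Section 8.9.1 sets a reporting window, not an analysis rule, and the synopsis promises only descriptive statistics for safety. This stands in part: the SAP may already contain a pre-rescue table. It is not a full answer, because Section 10.1 fixes the set, the parameters and the test, and provides for rescue only in efficacy.

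Second, counting all events in treated patients is a legitimate treatment-policy view of safety. That stands. A reader might infer that the all-events comparison should be replaced, or that the concern covers every event of special interest. Neither is supported. Replacement would demote later events, such as ketoacidosis after rescue in a luseogliflozin patient. It would also shorten observed time more on placebo, which raw frequencies in a Fisher test do not correct.

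Third, attribution is partly covered. Staff must ask about new concomitant treatment at each hypoglycaemia report (Section 8.6), a dedicated form is completed (Section 8.9.2.4), and IMP-related events are analysed separately. These help case review, but they do not supply a between-arm comparison free of rescue.

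**Conclusion.** The point holds for hypoglycaemia and, through it, for the pooled special-interest frequency. As written, the only stated comparison includes post-rescue events, and it is expected to favour luseogliflozin if rescue is more frequent on placebo and post-rescue risk is broadly similar across arms. A reader might infer that the placebo rate is inflated as a matter of fact and that luseogliflozin will look safer than it is. The protocol does not support that, because it contains no rescue or hypoglycaemia rates. Under the assumed ranges the shift runs from negligible (0.3 points) to enough to reverse a true excess (4.5 points, risk ratio 2.5 falling to 0.8). Without a pre-rescue analysis a reader of the results could not tell which applies. The primary efficacy analysis is untouched.

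**What to change.** In Section 10.1 or the SAP, before unblinding, prespecify a between-arm comparison of hypoglycaemia with onset from first IMP intake to the start of rescue medication, and show it beside the all-events comparison. Keep the all-events comparison for hypoglycaemia and for every other event of special interest. Because pre-rescue follow-up may differ by arm, also give exposure-adjusted rates. This mirrors the two analyses already planned for HbA1c.

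While editing, reconcile the synopsis (descriptive safety statistics) with Section 10.1 (Fisher tests), and make sure the start date is among the rescue details captured in the e-CRF.

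The cost is a sentence and one table set, with slightly less follow-up from rescued patients in that one analysis. No clinical rule changes. Adding the split after unblinding would look data-driven.

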Efficacy analysis:

In order to take into account the multiplicity of comparisons induced by the assessment of three luseogliflozin doses versus placebo, a Bonferroni correction will be used.

Primary endpoint

In order to meet the primary objective of the study, the efficacy of at least one dose of luseogliflozin as compared to placebo after 12 weeks of treatment in glycemic control will be assessed from the change from baseline to W12 in HbA1c, in patients of the RS.

Analysis of covariance (ANCOVA) will be used as the main method of assessment of the primary endpoint, with baseline (W0) HbA1c value being a covariate.

Unrestricted least significant differences (LSD) method will be applied to the ANCOVA results with the calculation of least-square (LS) means with 95% CI for LS means for the difference between each dose level and placebo.

Name of the sponsor: JSC Servier	Individual Study Table Referring to Part of the Dossier	(For National Authority Use only)
Name of Finished Product:	Volume:	
Name of Active Ingredient: Luseogliflozin	Page:	

Finally, to assess the dose-response of the investigation product with regards to the primary endpoint, contrasts will be built based on the ANCOVA results.

Before performing ANCOVA, a multiple imputation procedure will be used to impute:

- Missing data for the primary endpoint at 12 week (for patients with missing data at W8 and W12 and for patients with missing data at W12 only)
- Data collected after rescue therapy for non-controlled patients

This approach allow to evaluate, as primary analysis, the hypothetical « proper effect » of luseogliflozin without additional effect of rescue therapy.

Two additional analysis will be performed on the primary endpoint:

- Before performing ANCOVA, a multiple imputation procedure will be used to impute missing data for the primary endpoint at 12 weeks. Here data collected after rescue therapy will be taken into account in the analysis allowing to evaluate the effect of "the treatment policy" of luseogliflozin + rescue medication *versus* placebo + rescue medication.
- Last observation carried forward (LOCF) method will be used to impute post rescue evaluations and other missing data at 12 weeks for the primary endpoint (for a bridging objective with studies performed on Japanese population)

Study patients (disposition, baseline characteristics and follow-up) and safety analysis: Descriptive statistics will be provided.

Sample size rationale:

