8.2.2. Vital signs

HR and BP will be measured at all visits after at least 5 min rest. BP should be assessed in the sitting position using 2 measurements taken at least 2 minute intervals, preferably with an automatic blood pressure device. Blood pressure should be measured at the same arm and using the same device, throughout the study as far as possible. Both measurements should be reported in the e-CRF and the mean value will be automatically calculated.

Uncontrolled hypertension is defined as a mean of 2 measurements for systolic blood pressure >180 mmHg and/or for mean diastolic blood pressure >100 mmHg. The criteria will be rechecked at inclusion; if the values are over these limits, the patient must not be included.

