8.2.5. Laboratory assessments

The blood and urine samples will be assayed by a local laboratory (except HbAc1 measurements and urinary glucose, which will be done at central laboratory). Blood ketones will be assessed using test strips during the visit.

The blood tests must be obtained under fasting conditions (i.e., after the patient has fasted for ≥ 10 hours). Fasting is defined as nothing ingested by mouth except water (and any essential medications). If a patient is not fasting, the Investigator will reschedule the blood sampling within the visit timeframe window previously defined. Laboratory certification (including expiration date) and normal reference ranges for all required parameters used during the study will be enclosed in file with the Sponsor prior to study initiation. Local laboratory normal ranges values will be collected, as well as any update in these values during the study and must be documented on the corresponding page of the e-CRF.

Outside of normal range values should be assessed by the Investigator. The Investigator will exercise medical and scientific judgment in deciding whether an abnormal laboratory finding or other abnormal assessment is clinically significant.

The following parameters must be evaluated:

- Haematology: white cell count with differential formula (neutrophils, lymphocytes, monocytes, eosinophils, and basophils), red cell count, hemoglobin, hematocrit, and platelets count,
- Biochemistry: creatinine, eGFR (according to MDRD formula), total bilirubin, ALT, AST, total protein, sodium, potassium, chloride, total cholesterol, LDL cholesterol, HDL cholesterol, triglycerides, uric acid,
 - eGFR will be calculated in e-CRF using the MDRD formula (Modification of Diet in Renal Disease Study equation) (Levey, 2006): eGFR (mL/min/1.73 m2) = 175 × (serum creatinine in mg/dL) $^{-1.154}$ × (age in years) $^{-0.203}$ × (0.742 if female)
- Blood ketones using test strips
- Urine analysis: color, appearance, specific gravity, pH, protein, ketones, bilirubin, erythrocytes, leucocytes, nitrite, microscopic examination.

Haematology and biochemistry tests are to be performed at selection period and at W12 visit, blood ketones— at W0 and at every study visit including W14 visit, urine analysis — at selection period and at every study visit including W14. Abridged laboratory test (hematocrit; total bilirubin, ALT, AST, creatinine, eGFR, serum sodium, potassium, chloride) will be performed at W 4 and W8 visits.

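### The two-way ANOVA (group, visit) planned for laboratory, vital-sign and ECG values has no patient term, so its group tests are too liberal and its group-by-visit tests too conservative

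*Protocol*

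**What the plan says.** The Safety analysis part of protocol section 10.1 fixes the method: "Laboratory parameters, vital signs and 12-lead ECG data will be analysed using two-way ANOVA", or ANOVA on ranks if normality fails. Its stated purpose is "to account for group and visit factors simultaneously". No patient factor, random effect, within-patient covariance or baseline covariate is named.

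The measurement schedule (Table 1 and section 8.2) has each patient measured repeatedly:

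- Vital signs: "HR and BP will be measured at all visits after at least 5 min rest". That is W-2, W0, W4, W8, W12 and W14, or up to 6 values.
- Full laboratory panel: "Haematology and biochemistry tests are to be performed at selection period and at W12 visit". That is 2 values.
- Abridged laboratory parameters (haematocrit, bilirubin, transaminases, creatinine and eGFR, electrolytes): also at W4 and W8, so 4 values.
- ECG (section 8.2.3): selection and W12, so 2 values.

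Other safety data follow other rules in the same section: "Frequency data will be compared between the groups using exact Fisher tests", and "numeric data will be compared between the groups using the t-test or Wilcoxon-Mann-Whitney test on ranks".

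**The concern.** Values from one patient at different visits are correlated. A model with group and visit as its only factors counts them as separate observations and uses one residual variance for every test. That variance is wrong in both directions. It is too small for comparing groups on their average over visits, where patients are the independent units. It is too large for comparing change between visits, where stable differences between patients cancel.

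The protocol names BP, HR, ECG and laboratory parameters as secondary safety endpoints (section 4.1) and lists BP decrease within an adverse event of special interest (section 8.6). The analysis could therefore flag dose-placebo differences that are noise and miss real treatment-related changes over time.

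**Working it through.** **The plan's own figure.** The protocol gives no error rate or power for the safety ANOVA. Its one computable figure is the primary power of around 85% (section 10.2). With 80 per group, difference 0.6, SD 1.1 and two-sided alpha 0.05/3, this comes to 85.5% (normal) or 84.7% (noncentral t). It reproduces and does not depend on the safety model.

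**Inputs.** From the protocol: 4 groups of 80, two-sided 5%, and m = 2, 4 or 6 visits. The case m = 3 is added for W4, W8 and W12 only. Assumed, because the protocol gives none: equal correlation ρ between any two visits of a patient, with ρ from 0.4 to 0.7.

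**Group contrast averaged over visits.** Let σ² be the variance of a single value and n the patients per group.

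- ANOVA without a patient term uses variance 2σ²/(nm).
- The true variance is 2σ²[1 + (m−1)ρ]/(nm).
- True error of a nominal 5% contrast = 2 × [1 − Φ(1.96/√(1 + (m−1)ρ))].

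| Visits entering | 1 + (m−1)ρ at ρ = 0.4; 0.7 | 1.96 ÷ root | True error |
|---|---|---|---|
| 6 (vital signs, all visits) | 3.0; 4.5 | 1.13; 0.92 | 26%; 36% |
| 4 (abridged laboratory, all visits) | 2.2; 3.1 | 1.32; 1.11 | 19%; 27% |
| 3 (W4, W8, W12 only) | 1.8; 2.4 | 1.46; 1.27 | 14%; 21% |
| 2 (ECG, full panel) | 1.4; 1.7 | 1.66; 1.50 | 10%; 13% |

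**Change over time.** For the difference between two groups in change between two visits, the ANOVA uses 4σ²/n. The true variance is 4σ²(1−ρ)/n. The standard error is too large by 1/√(1−ρ): 1/√0.6 = 1.29 at ρ = 0.4 and 1/√0.3 = 1.83 at ρ = 0.7.

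**Check by a separate calculation over a wider range.** With ρ from 0.3 to 0.8, the dose-placebo error is 22-38% for 6 visits, 16-29% for 4 and 9-14% for 2. The four-group F test is at 37-67%, 25-51% and 11-22%. A simulation (4 × 80 patients, no true effect, 3,000 runs per setting) agrees closely. In it, the size of the group-by-visit test falls from 5% to about 1% or less. A test on patient means, which makes the patient the error unit, has size 4.4% to 5.4%.

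These sizes are for the ANOVA on untransformed values. Ranking does not remove the dependence between a patient's visits, but its effect on the ranked version was not computed.

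**The case against.** **Details may sit in the SAP.** Section 10.1 calls itself brief and leaves details to an SAP that is not at hand. The protocol does not say that visits are treated as independent, and it does not exclude a patient term. An SAP could treat visit as a within-patient factor. This limits what can be said: the fault lies in the sentence as written, and the final analysis may not carry it. It does not remove the point, because the sentence already names both the test and its factors. Unlike the secondary efficacy paragraphs, it is not expressly deferred to the SAP.

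**The size depends on which visits enter.** This stands. The 6-visit figure needs W-2, W0 and the off-treatment W14 visit all in the model. If only post-baseline visits entered, ECG and the parameters measured only in the full panel would have one value each, and their group test would have no within-patient correlation problem.

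Four stronger readings are tempting and are not supported:

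- *Every safety comparison is wrong.* Adverse-event and abnormality frequencies go to Fisher tests, and by-visit summaries use one value per patient per visit.
- *The plan pools pre-treatment with on-treatment visits and ignores baseline.* The protocol does not say which visits enter, or whether raw values or changes are analysed.
- *The safety conclusion will be misleading.* No safety hypothesis, decision rule or sample size rests on these tests.
- *The synopsis contradicts section 10.1.* The synopsis says "safety analysis: Descriptive statistics will be provided". It does not say that only descriptive statistics will be given, and a short summary line does not rule out tests described in the body.

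Choosing between tests by a Shapiro-Wilk result is a separate matter and no part of this point.

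**Conclusion.** The method is wrong as written and should be fixed. The fault is confined to ANOVA inference on laboratory, vital-sign and ECG values. Under an assumed within-patient correlation of 0.4 to 0.7, equal across visits, a nominal 5% dose-placebo contrast averaged over visits has a true error between about 10% (2 visits) and 36% (all 6). Contrasts of change over time err the other way. The direction holds for any positive correlation of this form; the size depends on the correlation and on the visits included, and the protocol states neither. The primary analysis and the sample size are untouched, so this ranks below faults that bear on the trial's main conclusion.

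**What to change.** In the Safety analysis part of section 10.1, and in the SAP, replace the two-way ANOVA with one of these:

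- a repeated-measures mixed model with the patient as the error unit, on post-baseline visits, with treatment, visit, treatment-by-visit and the baseline value as terms; or
- a per-visit ANCOVA on change from baseline.

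Where W12 is the only post-baseline visit (ECG and the parameters measured only in the full panel), use ANCOVA at W12. State which visits enter and whether values or changes are analysed.

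The cost is protocol and SAP wording and some programming before database lock. No new data or visits are needed, and the sample size does not change.
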